with supportive nutrition skill-building activities, for low-income populations.[101] It is the only government-funded program of this type in Canada. Between 2007 and 2017, households received \$15/week. This amount was determined based on a U.S. farmers' market coupon program that provided on average \$10-30 for participants [102] and based on the availability of funds. The amount increased to \$21/week in 2017 to account for increased food costs. In 2018, the BC FMNCP served over 11,000 individuals, including 532 pregnant women, 1,084 seniors, and 4,965 children.[103] The program facilitates access to nutritious foods for low-income families, pregnant women, and older adults by providing participants with coupons valued at \$21/week to purchase fruits, vegetables, dairy, meat/poultry/fish, eggs, nuts, and cut herbs from participating BC farmers' markets.[101] Farmers' markets that participate in the BC FMNCP operate 1-2 days per week, with hours that vary by location. While coupons may only be redeemed from June to November, most communities offer indoor markets that are open year-round.[101, 104] The goal of the BC FMNCP is to provide financial support for low-income households to purchase and consume healthier foods, thereby improving diet quality [47, 105] and overall health.[106, 107] The program also aims to minimize further marginalization of low-income individuals by encouraging their participation in farmers' markets, which are important social spaces that may foster social and mental well-being.[54, 108, 109] Currently, the FMNCP operates in 57 BC communities and reaches over 3900 households;[101] however, the need remains substantial, with over 15 communities on waiting lists to participate. It is unclear if the BC FMNCP is achieving its aims, as the program's outcomes have not been rigorously investigated.

This study was co-designed with the BC Association of Farmers' Markets and the FMNCP in order to achieve the following objectives:

- 1) Conduct a RCT to examine the impact of the BC FMNCP on the following outcomes immediately post-intervention and at 16 weeks post-intervention among low-income adults:

- a. mean overall diet quality (primary outcome);
- b. mean diet quality subscores, mental well-being scores, sense of community, odds of experiencing household food insecurity and odds of malnutrition risk (secondary outcomes); and
- c. mean subjective social status (exploratory outcome)

METHODS

Study design

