- Able to speak, read and write in English (or have someone who can assist them)
- No plans to move from principal residence prior to study completion
- Has not previously participated in the BC FMNCP

Randomization

Following baseline data collection, eligible participants will be randomized to the FMNCP group (n=132) or a no-intervention control group (n=132), with a 1:1 allocation ratio. An independent researcher from the Clinical Research Unit at the University of Calgary will generate a blocked randomization sequence that stratifies participants into blocks according to sex (male, female), geographic location (rural, urban), pregnancy (yes, no) and breastfeeding (yes, no). Blocked randomization will help to ensure balanced representation of participants in study arms.[110] REDCap (Research Electronic Data Capture), a secure, web-based data collection and management application [111] hosted at the University of Calgary, will be used to randomize participants into the FMNCP and control groups on the basis of this randomization sequence. The study coordinator will subsequently communicate participant group assignments to community partners and participants. Allocation concealment will be ensured via secure storage of the randomization sequence separately from the participant database, which will only be accessible by the study coordinator and the Clinical Research Unit. Researchers will remain blinded to respondent condition throughout the study. Although participants cannot be blinded to group allocation, they will be blinded to the specific study objectives to reduce expectancy bias, whereby communication of expected study outcomes influences participants' behaviour.[112-115]

Intervention

In the existing BC FMNCP, community partners distribute one to two sheets of coupons per week (each sheet contains \$21 in coupons) to program participants for a total of 16 sheets. Coupons can be used over 16-20 weeks to purchase fruits, vegetables, dairy, meat/poultry/fish, eggs, nuts, and cut herbs at participating BC farmers' markets. However, to allow sufficient time to recruit participants for this study, community partners will distribute 16 coupon sheets to the FMNCP group over 10-15 weeks (households with 5-8 individuals will receive 32 coupon sheets). To ensure participants receive all 16 coupon sheets,

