community partners will provide two coupon sheets per household during weeks 1-6 of the intervention. Participants may redeem coupons at farmers' markets at a frequency of their choice (e.g., redeem coupons weekly or redeem several weeks' worth of coupons simultaneously). Participants in the FMNCP group will be invited to participate in nutrition skill-building activities (e.g., cooking classes) offered by community partners throughout the intervention period, although participation is not required (this is consistent with the existing FMNCP). The types and frequency of nutrition skill-building activities offered vary across community partners. For the duration of the study, the control group will not receive coupons nor be eligible to participate in nutrition skill-building activities but will be eligible to participate in the BC FMNCP the following farmers' market season. As participants in the control group already receive other supports from community partners, they will continue to meet with their community partner as they normally would throughout the intervention period.

Data collection

Data will be collected from the FMNCP and control groups at three time points: Time 1: baseline (0 weeks), Time 2: immediately post-intervention (10-15 weeks), and Time 3: 16 weeks post-intervention (26-31 weeks). At each time point, participants will complete a questionnaire assessing sociodemographic characteristics, health-related variables, and secondary and exploratory outcomes, followed by a 24-hour dietary recall to assess diet quality. The questionnaire and dietary recall will be integrated within a web-based platform developed and pilot tested by the researchers [116]. A second dietary recall will be completed 2-5 days later to better estimate usual intake and account for within-individual variation in diet quality. All participants will receive cash incentives valued at \$20 at baseline and \$40 at each Time 2 and 3. Participants will also receive small gifts prior to data collection at Time 2 and 3, which will serve as a reminder for the upcoming data collection.

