Subgroup analyses will examine whether the impact of the intervention on primary and secondary outcomes differs according to age group or sex. Dose-response analyses will examine whether the impact of the BC FMNCP on overall diet quality depends on the number of coupons redeemed and the number of nutrition skill-building activities attended. Interactions will be retained in statistical models if $p < 0.10$. Analyses will be conducted in Stata (v15.1, Stata Corp, TX, USA), with $p < 0.05$ indicating statistically significant differences between groups.

Missing data

Missing data will be handled using full information maximum likelihood under a missing at random assumption. We will also attempt to minimize missing data by reviewing all data within 24 hours of receipt and by contacting participants to fill-in missing or implausible responses within 48 hours. Participants who drop out of the study will be asked to provide reasons for drop out to assess the plausibility of a missing at random assumption.

Sensitivity analyses

Monte Carlo Markov Chain multiple imputation, inverse probability weighting and available case analysis will be used in a sensitivity analysis to investigate the impact of different assumptions about missing data on estimated program impacts.[176-178] Given the possibility of non-random attrition, pattern mixture methods models [179] will be used to explore the robustness of study findings to the assumption that data were missing not at random.[180]

Sample size calculation

The sample size was calculated from a RCT that investigated the impact of a fruit and vegetable rebate on HEI-2010 scores in low-income participants in the U.S.,[95] and a cross-sectional study that assessed average diet quality scores in disadvantaged Canadians.[36] In the RCT, diet quality in the intervention group was 4.7 points higher (95% CI 2.4, 7.1) at follow-up compared to controls.[95] This difference can be translated to, for example, an additional half serving of fruit per day, which is clinically meaningful and achievable.[107, 165] Assuming a type I error of 5%, an attrition rate of 30% by the 26- to 31-week follow up, and potential design effects based on sampling within different communities (estimated at 1.1, or an inflation of 10%), 264 participants are required for 80% power to detect a 4.7-point difference in diet quality.

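### The dose-response analysis compares participants by take-up they chose after randomisation, so its gradient is an association and not evidence of what the programme's impact depends on

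*Combined protocol and SAP*

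**What the plan says.** The Statistical analyses section states: "Dose-response analyses will examine whether the impact of the BC FMNCP on overall diet quality depends on the number of coupons redeemed". The same sentence covers the number of skill-building activities attended. The section gives no model for this analysis, does not say how control participants enter it, and attaches no exploratory label or causal method. It also keeps interactions in models at p < 0.10.

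The Intervention section shows how the two doses arise:

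- Redemption: "Participants may redeem coupons at farmers' markets at a frequency of their choice".
- Attendance: FMNCP participants are invited, and taking part is optional. Supply also differs by site: "The types and frequency of nutrition skill-building activities offered vary across community partners".
- Controls: "the control group will not receive coupons nor be eligible to participate in nutrition skill-building activities".
- Allotment: "community partners will distribute 16 coupon sheets to the FMNCP group over 10-15 weeks", except that "households with 5-8 individuals will receive 32 coupon sheets".

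The main comparison is intention-to-treat, irrespective of whether coupons are redeemed. The listed covariates include the baseline value of the outcome and household size and, for HEI, age, sex, BMI, marital status, race/ethnicity, perceived health, smoking and children in the home.

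**The concern.** Asking what the impact depends on is a causal question. Randomisation protects the comparison of FMNCP with control. It does not protect a comparison of high redeemers with low redeemers. Since controls sit at zero apart from contamination, the dose slope is identified almost wholly from differences among FMNCP participants, and those differences are self-selected.

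The Background section supplies a candidate confounder. It says that higher self-efficacy for eating fruit and vegetables goes with higher intake. Self-efficacy is not in the questionnaire or the covariate list. That it also drives redemption is plausible but is not stated.

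Adjusting for baseline HEI helps only in part, because two recalls measure usual diet with error. The plan itself adds the second recall to deal with day-to-day variation.

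At stake is interpretation: a gradient produced by who chooses to redeem could be reported as the effect of more coupons or more classes.

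**Working it through.** **1. The plan's own figure.** The documents give no number for the dose-response analysis. The nearest is N = 264 (132 per arm) for a 4.7-point difference, 80% power, 5% type I error, 30% attrition and a design effect of 1.1. No SD is stated, so 264 cannot be reproduced independently, only solved backwards:

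- Effective n per arm = 132 × 0.7 / 1.1 = 84.
- SD = 4.7 × √(84/2) / (1.960 + 0.842) = 10.87, taking the test as two-sided.
- Observed n per arm after attrition = 132 × 0.7 = 92.4, taken as 92.

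Other readings of the inflation, still two-sided, give an SD of 11.40 to 11.52. A one-sided test with the inflation used above gives 12.25.

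**2. Simulation with a programme effect of exactly zero.** Baseline and follow-up HEI = 10.87 × (√rel × T + √(1 − rel) × noise), where T is true usual diet quality. Sheets redeemed = 11 + 5 × latent, limited to 0-16, in the FMNCP arm only, with corr(latent, T) = c. Follow-up HEI is regressed on group, baseline HEI and sheets. The values of c, the reliability (0.35-0.5) and the redemption distribution are assumptions.

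| c | Mean slope × 16 sheets | Slope significant at 0.05 |
|---|---|---|
| 0 | 0 points | 5% |
| 0.1 | about 1.4 points | about 6% |
| 0.2-0.5 | about 3 to 8 points | 12-49% |

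In the same data the randomised comparison rejects in about 5% of trials. If the dose term falls under the plan's p < 0.10 retention rule, it would be kept in 18-62% of trials at c = 0.2-0.5.

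**3. Sensitivity to the assumptions.** Adding one covariate assumed to explain 30% of true diet quality lowers the c = 0.2-0.5 results to 10-37% rejection and 2.3-6.4 points.

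A second set-up lets an unmeasured trait drive usual diet and redemption with equal correlations of 0.3, 0.5 or 0.7. The implied redemption-diet correlations are the products 0.09, 0.25 and 0.49 (0.3², 0.5², 0.7²). It includes 32-sheet households and adjusts for household size. Over baseline/follow-up correlations of 0.3-0.7:

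| Confounding | Points per 16 sheets | Rejection at 0.05 |
|---|---|---|
| weak (0.3/0.3) | 0.4-0.8 | 5-6% |
| moderate (0.5/0.5) | 1.3-2.0 | 10-12% |
| strong (0.7/0.7) | 2.8-4.1 | 27-33% |

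The mechanism and direction agree; the size does not transfer between set-ups.

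**4. Household count as a dose scale.** Each sheet is worth $21, so the full allotment is 16 × 21 = $336, or 32 × 21 = $672 for households of 5-8.

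| Household size | 1 | 2 | 3 | 4 | 5 | 6 | 7 | 8 |
|---|---|---|---|---|---|---|---|---|
| Dollars per person | 336 | 168 | 112 | 84 | 134 | 112 | 96 | 84 |

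A 32-sheet household thus has less per person than a one- or two-person household with 16. To see whether this alone creates a false gradient, self-selection was set to zero and household size was given an assumed effect on HEI:

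| Assumed household effect | Household size not in model | Household size in model |
|---|---|---|
| −1 point per person | −1.1 points, 7.7% | 0.0 points, 4.9% |
| −5 points at 5 or more people | −1.3 points, 9.0% | −0.5 points, 5.2% |

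**The case against.** The strongest reply is that this is a supporting analysis, absent from the listed objectives, and that the intention-to-treat comparison does not depend on it. That stands, and it limits the point to how one secondary result is specified and reported.

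A second reply is that the size is assumption-driven. That also stands. No document gives a redemption-diet correlation, a reliability for HEI or a redemption distribution. Weak confounding leaves rejection near 5%, and the bias would be negative if people with poorer diets redeemed more.

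Three stronger readings might be inferred, and the documents do not support them:

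- *Counting coupons per household itself produces a false gradient.* Household size is a planned covariate, and with it in the model rejection stays near nominal. This assumes that the main-model covariates carry into the dose-response model, which the text implies but does not state. The household count is a mis-scaled exposure.
- *Coupons redeemed after the Time 2 recall contaminate the dose.* The Background section says "coupons may only be redeemed from June to November", but this describes the existing programme, and Time 2 is defined as immediately after the intervention. The vendor and market records described are bar codes, checkboxes and counts, with no dates mentioned. The point should not be pressed unless redemption dates prove to be recorded.
- *The false gradient is as large as the 4.7-point target.* That needs strong assumed confounding. In the second set-up with both arms it is never reached.

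**Conclusion.** The concern holds in a limited form. As written, the analysis can attribute a self-selection gradient to the programme, because both doses are voluntary, arise after randomisation and are absent in controls by design. With no programme effect, the spurious slope runs from 0 points per 16 sheets (5% rejection) without self-selection, through about 1.4 points (about 6%) at a correlation of 0.1, to about 3 to 8 points (12-49%) at 0.2-0.5. These figures rest on an SD of 10.87 solved from N = 264, 92 per arm, reliability 0.35-0.5, an assumed redemption distribution and a model without the plan's further covariates, which would shrink them. They are illustrations of a mechanism and not forecasts for this trial.

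Nothing here shows that the primary result is biased or that the sample size is wrong.

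**What to change.** 1. Report the redemption and attendance gradients as exploratory associations, not as what the impact depends on. State how controls enter the model and which covariates it carries.
2. If a causal take-up question is wanted, add a complier-average estimate with randomised assignment as the instrument. In its simplest form it is the intention-to-treat difference divided by the difference in take-up between arms. Treat coupons and activities as one package, since a single binary instrument cannot separate them. Define take-up in advance as any receipt or attendance, so that people classed as untreated are not partly exposed. The Time 2 questions on coupon receipt and attendance are put to both arms and supply the data.
3. Optionally, as a secondary scaling, express redeemed coupon value per household member.

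The cost is a change of wording and one added model on data already collected. The instrumental estimate has a wider interval and does not estimate a dose gradient. If nearly everyone assigned takes up the programme and few controls do, it will sit close to the intention-to-treat result. Self-reported receipt will be missing for Time 2 non-responders, and the plan should say how they are handled.

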The HEI-2015 encompasses thirteen dietary components to assess overall diet quality,[161] including nine 'adequacy' components (recommended foods/nutrients, including total fruits, whole fruits, total vegetables, greens and beans, whole grains, dairy, total protein foods, seafood and plant proteins, fatty acids) and four 'moderation' components (foods/nutrients recommended to limit, including refined grains, sodium, added sugars, saturated fats). Component scores are density-based and, therefore,

independent of energy intake.[161, 163] Diet quality (total HEI-2015 scores and subscores) will be calculated using the simple HEI scoring algorithm.[161] This method provides scores at the individual level and can, therefore, accommodate the multi-level nature of our data and include covariates.[161] HEI-2015 scores will be calculated using three nutrient databases linked to the ASA24-Canada-2018:[173] the Canadian Nutrient File and the U.S. Department of Agriculture's (USDA) Food and Nutrient Database for Dietary Surveys to convert dietary intakes to energy and nutrient intakes, and the USDA Food Patterns Equivalents Database to convert dietary intakes to dietary constituents (e.g., fruits) and measurement units consistent with HEI-2015 scoring standards (e.g., cup-equivalents of fruit).[162, 163, 174, 175] Ratios for each of the dietary constituents (e.g., quantity of fruit per 1000 kcal) will be calculated for each participant and scored using HEI-2015 scoring standards. The total score for each participant will be derived by adding the scores for intake of 'adequacy' and 'moderation' components with possible scores ranging from 0-100. A higher score indicates a higher quality diet.[161]

Statistical analyses

Descriptive analyses will be conducted to examine participant characteristics by group at each time point. Characteristics of study completers (i.e., provided data at Time 3) and non-completers will also be compared.

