Analyses will be intention-to-treat, in which participants will be analysed within the groups to which they were randomized regardless of adherence (e.g., failure to redeem coupons) or dropout. The analyses will include all participants who provided data at baseline. Repeated measures mixed-effect regression will assess differences in changes in mean HEI-2015 scores, HEI-2015 subscores, mental well-being, sense of community, and subjective social status between the FMNCP and control groups immediately post-intervention and 16 weeks post-intervention. Multinomial logistic regression will be used to assess

differences in the odds of experiencing household food insecurity and malnutrition risk for the FMNCP group compared to the control group immediately post-intervention and 16 weeks post-intervention. Statistical models will include intervention group (FMNCP vs control), time from baseline, intervention-by-time interaction, blocking variables (i.e., sex, rural/urban, pregnancy, breastfeeding), baseline values of the outcome, data collection mode (online, phone), household size, and place of data collection (community partner, other) as fixed effects covariates. Participant-specific (i.e., repeated measures) and rural/urban variations in outcomes will be modeled using random effects. Models will also include covariates specific to each outcome to increase the precision of estimates.[95] For the primary outcome of overall diet quality, models will include children living in the home (yes, no), sex, age, BMI, marital status, race/ethnicity, perceived health, smoking, day of dietary recall completion, and dietary recall number (i.e., dietary recall 1 or 2). Models that are and are not adjusted for an indicator of energy intake misreporting (the ratio of reported energy intake to total estimated energy expenditure) will be presented. Adjusted group differences (i.e., FMNCP vs control) in outcomes will be estimated using 95% confidence intervals and corresponding p-values.

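### The p<0.10 retention rule lets the data choose the interaction terms in the outcome models, and gives no rule for reporting those that miss the screen

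*Combined protocol and SAP*

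**What the plan says.** All of this is in the Statistical analyses section, apart from the outcome list.

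- **Main model.** "Statistical models will include intervention group (FMNCP vs control), time from baseline, intervention-by-time interaction", followed by the blocking variables and further covariates, among them "baseline values of the outcome, data collection mode (online, phone), household size". No condition is attached to any of these terms.
- **Subgroups.** "Subgroup analyses will examine whether the impact of the intervention on primary and secondary outcomes differs according to age group or sex". The number of age groups and their cut-points are not given.
- **Dose-response.** For overall diet quality only, the plan asks whether the effect depends on coupons redeemed and on skill-building activities attended.
- **Retention.** The next sentence reads "Interactions will be retained in statistical models if" p<0.10. It names no particular interaction and exempts none.
- **Significance.** The sentence after that sets p<0.05 as "indicating statistically significant differences between groups".
- **Outcomes.** The objectives at the end of the Background list "mean overall diet quality (primary outcome") and "mean diet quality subscores, mental well-being scores, sense of community, odds of experiencing household food insecurity and odds of malnutrition risk (secondary outcomes"), each to be assessed immediately after the intervention and 16 weeks later.

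The plan gives no count of interaction tests and no multiplicity adjustment. It does not say whether a retained interaction enters the main model or a separate one, or how an interaction that is not retained will be reported.

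**The concern.** A rule that keeps or discards a term according to its own p-value makes the fitted model depend on the data. Two consequences follow.

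First, the meaning of the group coefficient can change. Suppose a group-by-sex or group-by-age-group term is kept in the outcome model. Under the usual reference coding, the coefficient for the intervention group then describes the reference category, and the plan does not say how the overall FMNCP effect would be recovered. Which quantity is reported as the effect on diet quality could turn on a secondary test at the 10% level.

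Second, the rule works as a filter on what the reader sees. Interactions that pass are kept; the plan is silent on the rest. Across many outcomes, some null interactions will pass by chance. Without the full set of estimates, a reader cannot judge how many were tried.

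**Working it through.** The plan states no figure for this point, so there is nothing of its own to reproduce. The steps below use its outcome list and thresholds.

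**1. What a retained term does to the group coefficient.** At a given time point, let G be the group (1 = FMNCP) and S a binary modifier such as sex (0 = reference). With the product term, the mean is b0 + b1·G + b2·S + b3·G·S.
- Effect when S = 0: b1.
- Effect when S = 1: b1 + b3.
- Overall effect, with a proportion q having S = 1: b1 + q·b3.

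The coefficient b1 therefore differs from the overall effect by q·b3 once the term is in the model. This holds under reference coding; centred coding would avoid it, but the plan specifies neither.

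**2. How often this would happen by chance for the primary outcome.** There are two modifiers (age group, sex), each screened at 0.10. If neither modifies the effect and the two tests are independent (an assumption):

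P(at least one retained) = 1 − 0.90² = 1 − 0.81 = 0.19.

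**3. Number of tests across the outcomes named for subgroup analysis.**
- Primary: 1 (total HEI-2015).
- Subscores: 13, since "The HEI-2015 encompasses thirteen dietary components to assess overall diet quality".
- Other secondary outcomes: 4 (mental well-being, sense of community, household food insecurity, malnutrition risk).
- Total: 1 + 13 + 4 = 18 outcomes.
- With 2 modifiers and one test each: 18 × 2 = 36.

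**4. Expected null terms if no true interaction exists.**
- Retained at 0.10: 36 × 0.10 = 3.6.
- Below the plan's 0.05 level: 36 × 0.05 = 1.8.

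These expectations do not require independence.

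**5. Chance of at least one null term being retained at 0.10.**
- All 36 independent: 1 − 0.90^36 = 0.977.
- Correlation 0.3 between the 18 outcomes within each modifier, modifiers independent: about 0.94.
- Correlation 0.5, same structure: about 0.87.

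The correlations are assumed; the plan gives none. At the 0.05 level with independence, the chance is 1 − 0.95^36 = 0.842.

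**6. Sensitivity of the count.** The figure of 36 rests on one test per outcome and modifier.
- Primary outcome only: 2 tests, 2 × 0.10 = 0.2 expected.
- Adding the two dose-response terms: 38 tests, 3.8 expected.
- Testing Time 2 and Time 3 separately: 72 tests, 7.2 expected.

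**The case against.** The strongest defence has three parts.

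*A 0.10 screen is a recognised convention for interaction tests, which have low power.* That is fair as a threshold for drawing attention to a result. It does not justify using the threshold to decide what is in the model or what is reported.

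*The subgroup and dose-response analyses are described as analyses in their own right, and adjusted group differences with 95% confidence intervals are promised separately. Nothing says that a subgroup model replaces the main one.* This stands in part: the change in meaning of the group coefficient arises only if the retained term enters the model that supplies the reported effect. But retention in the statistical models most naturally means exactly that, and the plan does not rule it out.

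*The expected count is of null terms retained, not of false findings declared.* This stands. Significance is set at 0.05, where the expectation is 1.8, and both figures assume no true interaction anywhere.

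A reader might also infer something stronger: that because the rule is unqualified, it would remove the intervention-by-time term whenever its p-value reached 0.10, and with it the primary result. The documents do not support that. The main model includes the term without condition, the retention sentence directly follows the subgroup and dose-response plans, and the objectives call for results at both follow-up times. What the term carries also depends on coding the plan leaves open. If baseline is only a covariate, the group main effect would survive the term's removal, and only the separate Time 2 and Time 3 estimates would be lost. The missing limit on the rule is an ambiguity to close, not a stated deletion.

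**Conclusion.** The concern holds on the narrow reading of the rule. As written, the rule makes the content of the outcome models depend on the data and leaves unretained interactions without any stated reporting. For the primary outcome, the chance of admitting at least one null subgroup term is 19%, assuming two independent null modifiers. Over 36 tests, 3.6 null terms are expected to be retained at 0.10 and 1.8 to fall below 0.05. Those figures assume no true interaction and one test per outcome and modifier, a count inferred from the outcome list because the plan gives none. The shift of the group coefficient to a reference-subgroup effect further assumes reference coding and that the retained term sits in the model used for the main estimate.

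This is a weakness in specification and reporting that can be removed at almost no cost. It does not show that the planned primary analysis is invalid.

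**What to change.** Replace the retention sentence with text to this effect:

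- The main model, including intervention-by-time, is fixed whatever the p-value of any interaction. The overall FMNCP effects at Time 2 and Time 3 are estimated from that model.
- Each prespecified subgroup interaction is fitted in a separate model. Dose-response terms likewise do not alter the main model.
- Every subgroup interaction estimate is reported with its 95% CI and p-value, whether or not p<0.10.
- These analyses are labelled exploratory, and the number of interactions tested is stated.

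The cost is a rewording and a longer subgroup table. No new data are needed, and the sample size is unaffected.
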